Each safety variable will be summarized descriptively. Adverse events (AEs) will be classified as treatment-emergent, based on treatment-specific exposure, or pre-treatment. Count and percentage will be provided by relationship to device, and separate tables will be generated for ocular and nonocular AEs. Counts and percentages in each grade category will be presented for each biomicroscopy parameter. Device deficiencies will also be tabulated. Supporting subject listings describing details of each safety variable will be provided. Listings describing details of AEs reported prior to usage of the study solutions will be presented separately from the safety analysis for the treatment-emergent AEs.

Sample Size Justification:

Sample size calculations for the primary endpoint are summarized below (one-sided $\alpha=0.05$).

Endpoint	Assumptions	Power	N
Primary			
CLDEQ-8	SD=10 (paired differences)	80% Detectable difference=3	36 per each of the 2 crossover sequences

[Redacted]

Sponsor:

Alcon Research, Ltd.
[name]
[name]

Protocol Number: LCO115-P001

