8 SUBJECT POPULATION

Approximately 120 subjects (approximately 8 to 20 subjects per site) are to be randomized at approximately 8 United States (US) sites to achieve approximately 110 subjects completed. An advertisement may be used to aid recruitment. The advertisement will be submitted to the IEC/IRB for approval. The IRB approved Pre-screening questionnaire will be provided before taking the consent.

The enrollment for the study is planned for 6 weeks. The expected duration of subject participation in the study (3 scheduled visits) is 30 ± 3 days per study period (up to 66 days total). The complete inclusion and exclusion criteria are presented in Section 8.1 and Section 8.2.

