11.4.1 Primary Efficacy

The primary objective of this study is to demonstrate superiority of OFPM when compared to HMPS in reducing dryness symptomatology as measured by CLDEQ-8.

The corresponding endpoint is the score (range 0 to 37) from CLDEQ-8, obtained by adding the numerical responses to each of the 8 items, collected at the Day 30 follow-up for each product (Visit 2 and Visit 3).

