11.4.1.2 Analysis Methods

A mixed effect repeated measures model will be fit to test these hypotheses, including terms for lens care solution, period, sequence group, and baseline CLDEQ-8 as fixed effects and subject as a random effect. Lens care difference (OFPM minus HMPS) and the corresponding one-sided 95% upper confidence limit will be provided.

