11.10 Sample Size Justification

Sample size calculation for each of the relevant efficacy endpoints is described below.

Primary Efficacy:

Sample size calculation for the primary efficacy hypothesis on decrease in symptomatology is based on published data (Chalmers 2012). With an assumed SD for paired differences of 10, a sample size of 36/sequence will provide 80% power to detect a difference of 3 at one-sided $\alpha=0.05$.

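### Is testing superiority at one-sided 0.05 a flaw, when the planned 110 completers would exceed 80% power even at one-sided 0.025?

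*Protocol*

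**What the plan says.** Protocol 11.4.1 sets out a single primary comparison: "The primary objective of this study is to demonstrate superiority of OFPM when compared to HMPS", measured by the CLDEQ-8 score at Day 30. The hypotheses in Protocol 11.4.1.1 and SAP 4.2.1 are directional, with the null that OFPM minus HMPS is zero or more. Protocol 11.4.1.2 and SAP 4.3.1 fit a mixed model and say that "the corresponding one-sided 95% upper confidence limit will be provided".

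The sample size sections (Protocol 11.10, SAP 7) start from an SD taken from published data, "With an assumed SD for paired differences of 10", and conclude that "a sample size of 36/sequence will provide 80% power to detect a difference of 3". The level, one-sided 0.05, is given there and in the synopsis.

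Protocol 8 sets the recruitment target separately. "Approximately 120 subjects (approximately 8 to 20 subjects per site) are to be randomized", and the aim is "to achieve approximately 110 subjects completed".

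Protocol 11.4.2 defines no secondary efficacy objective, and SAP 1.5 plans no interim analysis. Protocol 5.1 describes a market support study of a product used within its indication, with an effectiveness endpoint chosen from the findings of another post-approval study.

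**The concern.** Many statisticians expect a superiority claim to be tested at one-sided 0.025, the equivalent of two-sided 0.05. A one-sided 0.05 test corresponds to a two-sided 90% interval, so success could be declared when a two-sided 95% interval still includes no difference.

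A sponsor short of subjects might plead that the stricter level was unaffordable. Here the formal calculation asks for 72 completers and the plan provides about 110, so the stricter level seems to come almost free. The visible text gives no reason for 0.05 and no power for the primary endpoint at 110.

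The setting adds weight. The endpoint is subject-reported. Protocol 9.3 accepts that subjects cannot be fully masked, and the control is the subject's own product in commercial packaging. If expectation favours the new product, a lenient level makes a spurious claim easier. A one-sided limit also gives no bound on the other side, so a reader could not see the full range of plausible effects.

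**Working it through.** **Inputs.** SD of paired differences 10, difference 3, 80% power, one-sided 0.05, 36 per sequence (Protocol 11.10, SAP 7). About 110 completers and 120 randomized (Protocol 8). Two sequences, allocated 1:1 (Protocol 9).

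**Formula.** In a balanced 2x2 crossover with N completers, SE = SD/√N. Power is the probability that a noncentral t variable with N − 2 degrees of freedom and noncentrality 3/SE exceeds the critical t value.

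**Step 1: the plan's own figure.** For N = 72, SE = 10/√72 = 1.179 and the noncentrality is 3/1.179 = 2.546. The critical t at one-sided 0.05 with 70 df is 1.667. Power is 81.0%. The smallest N that reaches 80% is 71, which becomes 72 for equal sequences. The stated 36 per sequence is correct.

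**Step 2: power at both levels.** For N = 110, SE = 10/√110 = 0.953 and the noncentrality is 3.146.

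| Completers | Power, one-sided 0.05 | Power, one-sided 0.025 |
|---|---|---|
| 72 | 81.0% | 70.9% |
| 90 | 88.1% | 80.4% |
| 110 | 93.1% | 87.7% |
| 120 | 94.8% | 90.3% |

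So 110 completers do exceed 80% power at 0.025, where 90 would be enough.

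**Step 3: what the stricter level costs.** At 110 completers, type II error goes from 100 − 93.1 = 6.9% to 100 − 87.7 = 12.3%, a ratio of 12.3/6.9 ≈ 1.8. The reserve against a wrong planning assumption also shrinks:

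| Assumption (N = 110) | Power, 0.05 | Power, 0.025 |
|---|---|---|
| SD 10, difference 3 | 93.1% | 87.7% |
| SD 11, difference 3 | 88.4% | 80.9% |
| SD 12, difference 3 | 83.2% | 73.8% |
| SD 10, difference 2.5 | 83.2% | 73.8% |

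The last two rows agree because 3/12 = 2.5/10. Power stays at 80% up to an SD of about 11.1 at 0.025, and up to just under 12.6 at 0.05.

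**Step 4: what it buys.** The nominal false-positive rate halves, from 5% to 2.5%. The smallest significant observed difference moves from 1.659 × 0.953 = 1.58 to 1.982 × 0.953 = 1.89 points, a shift of 0.31 on a 37-point scale. Both are well below the planned difference of 3.

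**Step 5: the masking argument.** The documents give no size for expectation bias, so this is assumption only. With no true effect and SD 10, the false-positive rates at 110 completers are:

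| Assumed bias (points) | Level 0.05 | Level 0.025 |
|---|---|---|
| 0.25 | 8.3% | 4.5% |
| 0.5 | 13.1% | 7.5% |
| 1.0 | 27.3% | 17.9% |

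The stricter level lowers each figure but does not remove the inflation. At 0.5 points the rate is still 7.5/2.5 = 3 times nominal.

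**Step 6: is a one-sided limit the only interval planned?** In SAP 4.3.1 the sentence on the one-sided limit is followed directly by redacted text. The opening of Protocol 11 also allows confidence intervals or limits in continuous summaries where applicable. The visible text therefore does not establish that no two-sided interval will appear.

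**The case for a change.** The strongest case for the concern is this. Fixing the level in advance makes it honest but does not justify it. The documents give no reason for 0.05. Under their own SD and difference, the sponsor's 80% target is met at 0.025 with 20 completers to spare (110 − 90). The fall from 93.1% to 87.7% adds no subjects or visits. The endpoint is subjective and only partly masked, and success rests on one test, so caution is worth more than surplus power.

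Much of this stands. The figures are right, and a statistician who chose 0.025 here would be making a sound choice. If the 110 was set by an endpoint that is redacted, primary power at 110 is unchanged.

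The step from there to a defect does not stand. The margin is surplus only if the SD is close to 10, the difference is close to 3 and about 110 subjects complete. The SD comes from published data, so keeping a reserve against a larger one is a legitimate use of the extra subjects. The stricter level is also not a remedy for incomplete masking, as Step 5 shows. Nor is it a wording change: Protocol 1.1 puts the study in execution, and Protocol 7 requires a formal amendment with ethics approval unless a change is logistical, administrative or needed for immediate safety. It would alter the success threshold of a running trial.

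**Conclusion.** This is not a flaw in the plan. One-sided 0.05 is stated in advance and runs consistently through the directional hypotheses, the sample size and the confidence limit. The sample size claim is correct: 36 per sequence gives 81.0% against a stated 80%. With one primary endpoint, no secondary objective and no interim look, the visible efficacy plan does not spend this error rate elsewhere. No visible passage commits the study to 0.025.

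The choice between levels is a trade. At 110 completers, SD 10 and difference 3, the stricter level lowers the false-positive rate by 2.5 percentage points and raises the type II error by 12.3 − 6.9 = 5.4 points. If the SD is 12 or the difference 2.5, it takes power below the 80% target. Experienced statisticians could settle on either side for a post-approval market support study.

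Stating power at 110 and adding a two-sided 95% interval would help a reader, but would correct no wrong figure and change no result. The conclusion rests on the visible text. The redacted parts could hold further intervals or sample size reasoning, and their absence cannot be counted against the plan.

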11.4.2 Secondary Efficacy

[figure not shown]
No secondary efficacy objective is defined for this study.

[figure not shown]
11.4.2.1 Statistical Hypotheses

[figure not shown]
[figure not shown]
Not applicable

11.4.2.2 Analysis Methods

Not applicable

[figure not shown]

11.5 Handling of Missing Data

All data obtained in evaluable subjects/eyes will be included in the analysis. No imputation for missing values will be carried out for the efficacy analysis.

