8. History of herpetic keratitis, ocular surgery, or irregular cornea.
9. A pathological dry eye that precludes contact lens wear.
10. Use of mechanical eyelid therapy or eyelid scrubs within 14 days before Visit 1 and not willing to discontinue during the study.
11. Enrollment of the Investigator or his/her staff, family members of the Investigator, family members of the Investigator's staff, or individuals living in the households of these individuals.
12. Enrollment of more than 1 member of the same household in the study.
13. Participation in any clinical study within 30 days of Visit 1.
14. Subjects who are currently using or have not discontinued

Sponsor: Alcon Research, Ltd. Protocol Number: LCO115-P001
[name]
[name]

Restasis®, Xiidra® or a topical steroid within the past 7 days.

Assessments:

- CL-induced dryness symptoms as measured by CLDEQ-8
- Symptomatology pre-screening questionnaire
- [REDACTED]
- [REDACTED]
- [REDACTED]
- [REDACTED]
- [REDACTED]
- [REDACTED]
- Biomicroscopy
- Snellen visual acuity
- AEs and device deficiencies

Statistical Methods: Planned Analysis

Three analysis sets will be defined: safety, full, and per protocol (PP). The safety analysis set will include all subjects/eyes exposed to any study lens care products evaluated in this study. The full analysis set (FAS) is the set of all randomized subjects who are exposed to any study lens care products. The PP analysis set is a subset of all randomized subjects and excludes those who meet the critical deviation criteria as specified in the Deviations and Evaluability Plan (DEP). The FAS will serve as the primary analysis set for all efficacy evaluations.

All data from evaluable subjects will be included in the efficacy analysis; no imputation for missing values will be performed.

Efficacy:

To address the primary efficacy objective, planned analyses are summarized below.

Endpoint	Comparison	Statistical Method
PRIMARY		
CLDEQ-8 (Day 30)	OFPM vs HMPS Superiority	Mixed effect repeated measure model. Baseline score as a

Sponsor:

Alcon Research, Ltd.
[name]
[name]

Protocol Number: LCO115-P001

		covariate.
--	--	------------

[Redacted]

[Redacted]

[Redacted]

Safety:

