11.1 Subject Evaluability

The final subject evaluability will be determined prior to breaking the code for masked lens care sequence assignment and locking the database.

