11.2.2 Full Analysis Set

The FAS is the set of all randomized subjects who are exposed to at least one of the study lens care products as defined for the Safety Analysis Set.

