11.2.3 Per Protocol Analysis Set

The PP analysis set is a subset of all randomized subjects and excludes all data/subjects which have met any of the critical deviation criteria identified in the DEP.

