11.4 Efficacy Analyses

This study defines one primary endpoint [REDACTED] All efficacy evaluations will use the FAS as the primary analysis set. [REDACTED]

[REDACTED]

[REDACTED]

For all planned inferential analyses, alternative models/methods may be considered if convergence cannot be achieved.

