### **2.2            Full Analysis Set**

The Full Analysis Set (FAS) will consist of all randomized subjects who are exposed to at least one of the study lens care products as defined for the Safety Analysis Set. Each subject will be classified according to the respective lens care products in the randomized lens sequence, irrespective of the exposure. FAS will serve as the primary analysis dataset for all efficacy evaluations.

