### **2.3            Per Protocol Analysis Set**

The per-protocol (PP) analysis set is a subset of all randomized subjects and excludes all data/subjects which have met any of the critical deviation or evaluability criteria identified in the Deviations and Evaluability Plan. Each subject will be classified according to the respective lens care products in the randomized lens sequence, irrespective of the exposure.

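### Does the term evaluable in protocol section 11.5 and the synopsis replace the Full Analysis Set as the primary efficacy population?

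*Protocol*

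**What the plan says.** The protocol defines the FAS in section 11.2.2: "The FAS is the set of all randomized subjects who are exposed to at least one of the study lens care products". Section 11.4 adds "All efficacy evaluations will use the FAS as the primary analysis set", and SAP section 2.2 agrees: "FAS will serve as the primary analysis dataset for all efficacy evaluations". The synopsis and SAP section 4 also name the FAS as primary for efficacy. None of these places attaches an evaluability condition.

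The word *evaluable* appears in the missing-data text. Section 11.5 reads "All data obtained in evaluable subjects/eyes will be included in the analysis" and is followed by a sentence ruling out imputation for efficacy. The synopsis puts both ideas in one sentence, directly after naming the FAS as primary: "All data from evaluable subjects will be included in the efficacy analysis; no imputation for missing values will be performed".

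Evaluability is also a formal step. Section 11.1 says "The final subject evaluability will be determined prior to breaking the code for masked lens care sequence assignment and locking the database". The per-protocol (PP) set in protocol 11.2.3 "excludes all data/subjects which have met any of the critical deviation criteria identified in the DEP". SAP 2.3 words the same exclusion as "critical deviation or evaluability criteria identified in the Deviations and Evaluability Plan".

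**The concern.** Two labels seem to govern the same analysis. One is the FAS: everyone randomized and exposed. The other is the evaluable subjects, a status settled in a review before unmasking, whose criteria the SAP uses to thin the PP set. If the second label controlled the primary model, the superiority claim would rest on a subset chosen after randomization.

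Settling evaluability before the code is broken guards against deliberate selection. It does not remove bias if deviations depend on which solution was used. That is possible here: protocol 9.3 concedes that subjects cannot be fully masked, and CLDEQ-8 is self-reported. Two analysts reading different sections might then analyse different subjects.

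A smaller point concerns early exits. Protocol 10.4 has subjects who leave early undergo the Visit 3 procedures, which include CLDEQ-8, and the visible text does not say whether that score enters the primary model.

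**Working it through.** **Reading the passages together**

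1. *Which set is primary?* Four statements name the FAS, across both documents. No statement names an evaluable set as primary, and no evaluable set appears among the three analysis sets.
2. *What does section 11.5 do?* It says that evaluable subjects' data go in. It does not say that other FAS data come out. It stands under a missing-data heading next to the no-imputation rule, so its natural job is to say that observed data are used as they are. It also refers to eyes, although CLDEQ-8 is scored per subject. The safety set is defined for subjects and eyes, so this looks like standard text meant to serve several sets.
3. *Where are evaluability criteria applied?* In the visible SAP, only in the PP definition. Applying them to the FAS as well would erase much of the difference between the two sets, leaving little reason to define both.
4. *Does the SAP repeat the sentence?* Not in its visible text.

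**The plan's own figure**

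Inputs (protocol 11.10, SAP 7): SD of paired differences 10, difference 3, one-sided alpha 0.05, 36 per sequence. A one-sided t test on within-subject differences (noncentral t, N − 2 degrees of freedom) gives 80.95% power at N = 72, so the stated 80% reproduces. With the same inputs, power is 94.8% at 120 subjects, 93.1% at 110 and 88.1% at 90. Power is not at stake under either reading.

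**What the unlikely reading would do**

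The documents give no count of non-evaluable subjects, so both inputs here are assumptions: m subjects removed out of 120, whose OFPM-minus-HMPS difference is g points worse than in those kept.

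Shift towards OFPM = (m/120) × g. Rejection rate when the true FAS difference is 0: noncentral t, n = 120 − m, SD 10, one-sided 5%.

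| m | g = 0 | g = 3 | g = 6 |
|---|---|---|---|
| 6 | 0; 5.0% | 0.15; 6.9% | 0.30; 9.2% |
| 12 | 0; 5.0% | 0.30; 9.1% | 0.60; 15.3% |
| 18 | 0; 5.0% | 0.45; 11.6% | 0.90; 22.9% |

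The last cell assumes 15% removed with a gap twice the planned effect. A gap in the other direction moves the estimate against OFPM.

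**Early exits**

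About 120 − 110 = 10 subjects (8.3%) are expected not to complete. Take an extreme case: all 10 leave while on OFPM, each scoring 9 points above completers, with a completer difference of −3, 60 per sequence and no baseline covariate.

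- All leave in Period 2: one sequence's mean difference moves by (10/60) × 9 = 1.5. Averaging over the two sequences gives 0.75, so −3 becomes −2.25.
- All leave in Period 1: the shift is 0.75 × (1 − ρ), where ρ is the within-subject correlation. For ρ from 0.7 to 0.3 this is 0.225 to 0.525, giving −2.775 to −2.475.

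These figures show how far such scores could move the estimate if they were used. They do not show an error in the stated analysis, whose endpoint is the score at the Day 30 follow-up for each product (protocol 11.4.1, SAP 4.1).

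**The case for a change.** The best case for acting is that *evaluable* is not a casual synonym in this plan. Section 11.1 makes it a formal determination and SAP 2.3 makes it a ground for exclusion. The visible SAP has no missing-data rule of its own, so the protocol sentences are the only visible instruction that pairs missing data with a population, and both use this word. Changing it would cost almost nothing.

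Part of this stands: the term is undefined in the visible text and sits awkwardly beside the FAS. Wording such as *subjects or eyes in the relevant analysis set* would be tidier. But the case does not show that the plan directs a wrong analysis. A general sentence that includes data does not override explicit set definitions. The Deviations and Evaluability Plan, the obvious home for a definition, is not among the documents, and text close to the FAS statements in protocol 11.4 and SAP 4 is blacked out, so a missing definition cannot be held against the plan.

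On early exits, a sensitivity run using those scores is a defensible extra. It would mix shorter exposures with Day 30 scores, so statisticians could reasonably differ on its value. SAP text following the primary model is also redacted.

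**Conclusion.** The concern does not hold as an error. Following the plan gives a FAS analysis of the primary endpoint, with observed data and no imputation. Clearer wording would state the same intent and leave the estimate, its confidence limit and the power unchanged. The shifts of 0 to 0.90 points, and the rejection rates of 5.0% to 22.9%, depend wholly on assumed counts and gaps under a reading that the SAP does not support; they are not evidence of bias in this plan. The early-exit question is optional analysis, not a defect. This conclusion rests on the visible text and would need another look only if the Deviations and Evaluability Plan applied evaluability criteria to the FAS itself.

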11.7 Safety Analysis

The safety endpoints for this study are AEs, biomicroscopy findings, and device deficiencies.

Descriptive summaries (counts and percentages) for ocular and nonocular AEs will be presented by Medical Dictionary for Regulatory Activities (MedDRA) Preferred Terms. In addition to an overall presentation of AEs, reports will be generated for serious AEs. AEs leading to study discontinuation will be identified. Individual subject listings will be provided, as necessary.

Individual subject listings will be provided for AEs that occur after signing informed consent but prior to exposure to study lens care solutions.

Each biomicroscopy parameter will be tabulated by its grade. For each biomicroscopy parameter, counts and percentages of eyes that experience an increase of ≥ 2 grades from baseline to any subsequent visit will be presented. Baseline is defined as Visit 1. A supportive listing will be generated which will include all biomicroscopy data from the affected visit for those eyes experiencing the increase of ≥ 2 grades, with the following variables: lens care solution, Investigator, subject, age, sex, visit, eye, parameter, baseline value, and value at the visit.

Two listings (prior to exposure of investigational products, and treatment-emergent) of device deficiencies, as recorded on the *Device Deficiency* Form, will be provided. Additionally, each device deficiencies category will be tabulated.

No inferential testing will be done for safety analysis.

